
Test Product, Dose and Mode of Administration:
	
F901318 will be provided as an oral formulation.
 
This is a Phase IIb protocol and the dosing regimen for F901318 may be updated during the study. The dosing regimen for adults who are not being treated with medications that either inhibit or induce CYP enzymes will be a 1-day oral loading dose regimen of 150 mg F901318 bid, dosed 12\pm1 hours apart, followed by a maintenance dose regimen of 90 mg bid, dosed 12\pm1 hours apart, for Day 2 onwards. As this is the first study in which F901318 has been administered to patients, the target dosing regimen may need to be revised based upon emerging data, to ensure that the majority of patients achieve target plasma levels from the start of treatment. The revision to target doses will be captured in the Dose Guidance Manual. The dosage regimen will be determined from the Dose Guidance Manual (and following discussion with the MM if necessary).
 
 An adjustment to loading and/or maintenance doses of F901318 may be required for patients who are being treated with drugs that either inhibit or induce CYP enzymes (or if such drugs are started or stopped); treatment of these patients must be discussed with the MM. An adjustment to the maintenance dose of F901318 may be required if patients develop abnormal liver enzymes; treatment of these patients must be discussed with the MM. Based upon clinical evaluation of efficacy by the Investigator, stepwise increases of maintenance doses of F901318 (to 120 mg bid then 150 mg bid) may be permitted, following discussion with the MM. 
No dietary restrictions around time of dosing will be applied, although timing of meals or enteral feedings prior to each trough PK sample, and prior to and during Intensive PK sampling will be documented.

Reference Therapy, Dose, and Mode of Administration:
	
This is an open-label study and results will be compared with historical data.

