5.0 STUDY TREATMENTS

5.1 Treatments Administered

The investigational product in this study is F901318 (olorofim). This is an open-label study in which F901318 is given to eligible patients for up to 90 days during the main study phase (see Figure 1). Open-label treatment with F901318 may be continued beyond Day 90 in patients who are considered likely to continue to benefit from ET with F901318 (see Figure 2).

[REDACTED] dosing regimen for adults has been simplified to 150 mg bid (dosed at 12 ± 1 h intervals) followed by a maintenance dose regimen of 90 mg bid (dosed at 12 ± 1 h intervals) for Day 2 onwards. Nonetheless, and as this is the first time F901318 has been administered to patients, the target oral dosing regimen may yet need to be revised based upon emerging data, to ensure that the majority of patients achieve target plasma levels from the start of treatment. Any such revision to target doses will be captured in the Dose Guidance Manual.

The maximum total daily dose of F901318 is 300 mg, given as 2 doses (dosed at 12 ± 1 h intervals). Detail of the dosing regimen (number of tablets to be administered and the frequency of administration) will be provided in the Dose Guidance Manual. The recommended maintenance dose regimen may change during the study and current guidance should be confirmed with the MM at study initiation.

An adjustment to loading and/or maintenance doses of F901318 may be required for patients who are being treated with drugs that either inhibit or induce CYP enzymes (or if such drugs are started or stopped); treatment of these patients must be discussed with the MM. An adjustment to the maintenance dose of F901318 may be required if patients develop increased liver enzymes and/or bilirubins (See Appendix 3); treatment of these patients must be discussed with the MM. Adjustment to the maintenance dose may also be required if trough plasma levels of F901318 are outside the target range (as defined in the Dose Guidance Manual); treatment of these patients must be discussed with the MM.

Adjustment to the dose may be required if an Investigator considers the clinical response to be sub-optimal, where after discussion with the MM, dose increments may be implemented as follows:

1. [REDACTED]

[REDACTED]
[REDACTED] Blood sampling for evaluation of liver function must always be consistent with the Liver Biochemistry Management Algorithm as described in Appendix 3.

Dose Interruptions

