5.7 Trough PK Sample Analysis

Therapeutic drug monitoring for F901318 with dose adaptations to maintain optimal trough levels within a pre-specified target range will no longer be used. Rapid analysis of trough levels of F901318 will remain to monitor the potential impact of concomitant medication upon F901318, to have access to systemic exposure [REDACTED] and to support ongoing analysis of the safety profile of F901318 across the population.

The Sponsor is responsible for setting up regional hubs for rapid trough PK analysis, each of which will have access to a suitably validated F901318 assay. Sample collection to receipt at the regional hub will ideally take no more than 1 working day, with analysis being completed within 1 working day of sample receipt (i.e. 2 working days turnaround time between sample collection and trough PK data availability).

Guidance for dose adjustment (for use by the MM and PK consultant) will be available prior to study start and will accommodate dosing regimen changes due to concomitant medication, clinical judgement in response or when elevations in liver function tests occur which meet or exceed the threshold defined as moderate in Appendix 3 of the protocol. Should any dose adaptations be required, the MM and/or PK consultant will advise of any additional Unscheduled Trough PK sampling requirements, to enable the impact of the dose adaptation to be assessed.

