Samples shipped to the regional hub for rapid trough PK analysis (Scheduled and Unscheduled Trough PK samples) will be tested for F901318 alone. All PK samples (Scheduled and Unscheduled Trough PK, Intensive PK) will be shipped to the appropriate central laboratory and will be tested for both F901318 [REDACTED]

Rapid trough PK analysis:

Regional hubs will set up by the Sponsor for the rapid analysis all predose PK samples for F901318 (both Scheduled and Unscheduled). Dose adaptations may only be made in consultation with the MM when concomitant medications are required and the Investigator suspects there may be a risk of a clinically relevant DDI or when the Investigator believes there may be sub-optimal therapeutic response with the current dose or where elevated liver function results suggest a dose reduction is appropriate. Permitted and excluded concomitant medications are defined in the protocol.

Concomitant Medications:

PK sampling requirements when F901318 is given concomitantly with either a sensitive CYP3A substrate, a CYP3A inducer, a CYP3A inhibitor or other antifungal medication are detailed in Section 5.9.1.4.

6.6

[REDACTED]

[REDACTED]

[REDACTED]

[REDACTED]

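### Protocol 5.1 keeps an out-of-range trough as a reason to adjust the maintenance dose, while 5.7 says trough-targeted adaptation is no longer used and 6.5 does not list it

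*Protocol*

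**What the plan says.** Section 5.1 (Treatments Administered) deals in turn with CYP-inhibiting or CYP-inducing drugs, raised liver enzymes or bilirubin, and trough level. On trough it says: "Adjustment to the maintenance dose may also be required if trough plasma levels of F901318 are outside the target range". The range is the one in the Dose Guidance Manual, and these patients must be discussed with the MM. The section then adds sub-optimal clinical response as a further reason.

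Section 5.7 (Trough PK Sample Analysis) opens by saying that therapeutic drug monitoring "with dose adaptations to maintain optimal trough levels within a pre-specified target range will no longer be used". The assay itself stays: "Rapid analysis of trough levels of F901318 will remain to monitor the potential impact of concomitant medication upon F901318". The other visible purposes are access to systemic exposure and population-level safety analysis. The adjustment guidance for the MM and PK consultant "will accommodate dosing regimen changes due to concomitant medication, clinical judgement in response or when elevations in liver function tests occur".

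Section 6.5, under rapid trough PK analysis, begins "Dose adaptations may only be made in consultation with the MM when concomitant medications are required" and a clinically relevant interaction is suspected. It ends with "sub-optimal therapeutic response with the current dose or where elevated liver function results suggest a dose reduction is appropriate".

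The Synopsis entry on test product and dose lists CYP-active drugs, liver enzymes ("An adjustment to the maintenance dose of F901318 may be required if patients develop abnormal liver enzymes") and clinical evaluation of efficacy. It also says: "The dosage regimen will be determined from the Dose Guidance Manual".

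**The concern.** Sections 5.1 and 5.7 address the same act, changing a patient's dose because a trough lies outside a pre-specified range. One allows it after discussion with the MM. The other says it has been discontinued.

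The situation can occur in practice. Troughs are still collected throughout treatment, and 5.7 aims for results within two working days of collection, so an out-of-range value can be available while the patient is still on drug.

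What is at stake is conduct and the classification of deviations:

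- Section 5.11 requires departures from the intended regimen to be recorded in the eCRF.
- Section 7.0 asks the site, the monitor, the MM and data management to identify deviations.
- Neither says whether a dose change made for an isolated trough is compliant or a deviation.
- SAP 5.5 removes patients with major or critical deviations that affect efficacy from the per-protocol set, after case-by-case review, and SAP 16.1.4 repeats the primary analysis in that set. Classification could matter there if such a change were graded major or critical.

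**Working it through.** No formula or power figure is involved. The check sets the sections side by side, using only visible text now in force. The amendment log is not relied on.

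**Step 1. Reasons for a dose change, by section.**

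| Reason | 5.1 | 5.7 guidance | 6.5 | Synopsis (visible list) |
|---|---|---|---|---|
| CYP-active or interacting medication | yes | yes | yes | yes |
| Liver test elevation | yes | yes | yes | yes |
| Sub-optimal response | yes | yes | yes | yes |
| Trough outside target range | yes | no | no | no |
| **Total** | **4** | **3** | **3** | **3** |

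Difference: 4 − 3 = 1, which is trough level.

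**Step 2. Is trough a separate reason in 5.1?** Yes. CYP-active drugs and liver tests each have their own sentence, and trough follows as an additional reason with its own criterion and its own requirement for MM discussion. It cannot be read as shorthand for a suspected interaction.

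**Step 3. Does 5.7 merely omit trough?** No. Besides leaving it out of the guidance, its opening sentence withdraws the practice. The firm conflict is therefore one sentence in 5.1 against one in 5.7.

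**Step 4. How much do the other places add?** Section 6.5 supports 5.7, because its list does not include trough. The Synopsis adds little: its wording is permissive, the list is not stated to be exhaustive, it defers to the manual, and nearby text on rapid PK analysis is redacted. Its silence is not read as a prohibition.

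**Step 5. Do redactions explain the conflict?** Parts of 5.1 and 5.7 are blacked out, but the two conflicting sentences are complete. Hidden text could add detail; the visible sentences would still disagree.

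**Step 6. How often can it arise?** The Synopsis schedules main-phase troughs on Days 10, 14, 21, 28, 42, 56 and 70 and at Day 84/EOT, which is 7 + 1 = 8 time points, plus each extended-treatment visit. For a patient who stops at the last main-phase point no later dose remains to adjust, so 8 − 1 = 7 are relevant. The proportion of troughs outside the range cannot be estimated from the documents.

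**The case against.** The strongest reply is that no site can act alone. Section 5.1 requires MM discussion for this reason, and 5.11 requires MM approval of investigator-initiated regimen changes that result from clinical assessments. This does limit inconsistency between sites. It does not tell the MM which section governs, and the guidance that 5.7 describes for the MM does not name trough. What the MM is told in practice may be in the Dose Guidance Manual or the separate adjustment guidance, neither of which is available here.

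Second, the word *only* in 6.5 may govern the consultation rather than close the list of reasons, and the 5.7 guidance is not stated to be exhaustive. Both points are fair. They weaken the supporting count but leave the 5.1 and 5.7 sentences in conflict.

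Third, the consequences are limited. Departures are recorded whichever section governs, so no data are lost. The primary analysis uses the mITT set (SAP 5.4 and 16.1.3), which excludes nobody for deviations. Per-protocol exclusions are reviewed case by case. Where a CYP inhibitor is co-administered, a dose change already falls under the interaction reason. All of this stands, and it confines the problem to an isolated out-of-range trough.

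**Conclusion.** The concern holds. Two current, unredacted sentences of the protocol give opposite positions on whether an out-of-range trough may lead to a change of maintenance dose, and nothing visible resolves them. The inconsistency is in an operative dosing rule, so it should be corrected, although its reach is narrow: one reason out of four, and only when no interaction, liver or response concern is present.

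Confidence is high for the contradiction itself. Its practical effect is not established. The target range and any out-of-range rate are not in the documents, so the number of patients affected is unknown. The primary mITT result is not affected through deviation-based exclusions; among the analyses discussed, the per-protocol repeat is the one that could be. The conclusion assumes that the redacted passages and the Dose Guidance Manual contain no statement overriding one of the two sections. If they do, the visible sections still need to match it.

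**What to change.** Reconcile section 5.1 with 5.7, 6.5 and the Synopsis so that a single rule states whether an isolated out-of-range trough may be a reason to change the maintenance dose. Check that the Dose Guidance Manual and the guidance used by the MM and PK consultant say the same. Which rule applies is for the sponsor to decide; this review does not propose one.

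The cost is protocol wording in the next amendment or a clarification letter. Data collection, the sampling schedule and the SAP need no change. If dosing has already finished, a short documented interpretation would still settle how any past trough-driven change is classified.

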5.2 Identity of Investigational Products

Details of the F901318 dosage form used in this study are provided in Table 4.

Table 4 Investigational Products

Investigational product	Formulation	Dosage form and strength	Manufacturer
F901318	Oral tablet	30 mg per tablet	[REDACTED]

F901318

The oral formulation used in this study is a tablet containing 30 mg F901318 and standard pharmacopoeial excipients; [REDACTED]

The oral product should be stored and transported refrigerated (2-8°C).

[REDACTED]

5.3 Packaging and Labelling

The F901318 tablet will be packed into 64 count, 50 mL high density polyethylene bottles, with polypropylene twist off caps containing desiccant. Each bottle will have an approved clinical study label that complies with local regulations.

5.4 Method of Assigning Patients to Treatment Group

This is a single-arm, open-label, Phase IIb study. Patients who have provided informed consent, met all inclusion criteria and not met any exclusion criteria will receive treatment with F901318. The study centre will request the study drug assignment using the Interactive Web Response System (IWRS).

All patients will be managed by IWRS. The study centre will contact IWRS and patients will be assigned their 8-digit patient number by the IWRS at the time of enrolment. The IWRS will provide the medication kit/bottle number(s) of the study drug to be dispensed.

5.5 Selection of Doses in the Study

Based on data from clinical pharmacology PK studies, preliminary PK data from the ongoing study and Population PK modelling predictions, the dose of F901318 selected for this study is predicted to provide sustained and stable exposure to systemic concentrations of F901318 within the range expected to be effective against the target pathogens [REDACTED]

5.6 Selection and Timing of Dose for Each Patient

The recommended regimen will be as described in Section 5.1. The recommended regimen may change during the study and current guidance should be confirmed with the MM at study initiation.

There are no dietary restrictions associated with timing of F901318 dosing. If the patient vomits after taking oral F901318, the patient should not repeat the dose but should wait until the next dose as scheduled. Any patient who vomits twice in 1 day should inform the Investigator.

The time at which each dose is taken will be recorded in a patient dosing diary. The diary must be completed for hospitalized patients as well as for outpatients.

5.7 Trough PK Sample Analysis

Therapeutic drug monitoring for F901318 with dose adaptations to maintain optimal trough levels within a pre-specified target range will no longer be used. Rapid analysis of trough levels of F901318 will remain to monitor the potential impact of concomitant medication upon F901318, to have access to systemic exposure [REDACTED] and to support ongoing analysis of the safety profile of F901318 across the population.

The Sponsor is responsible for setting up regional hubs for rapid trough PK analysis, each of which will have access to a suitably validated F901318 assay. Sample collection to receipt at the regional hub will ideally take no more than 1 working day, with analysis being completed within 1 working day of sample receipt (i.e. 2 working days turnaround time between sample collection and trough PK data availability).

Guidance for dose adjustment (for use by the MM and PK consultant) will be available prior to study start and will accommodate dosing regimen changes due to concomitant medication, clinical judgement in response or when elevations in liver function tests occur which meet or exceed the threshold defined as moderate in Appendix 3 of the protocol. Should any dose adaptations be required, the MM and/or PK consultant will advise of any additional Unscheduled Trough PK sampling requirements, to enable the impact of the dose adaptation to be assessed.

5.8 Blinding

This is an open-label study. Study data reviewed by the DRC and Independent Data and Safety Monitoring Board (IDSMB) will not be blinded.

5.9 Prior and Concomitant Treatments

Prior medications associated with the initial management of the study-qualifying fungal pathogen will be recorded in the eCRF. All other anti-fungal medication taken during the 6 months prior to study screening will be recorded in the eCRF. The reason for antifungal medication and the outcome of treatment will also be recorded. Chemotherapy regimens (summary only) taken during the 12 weeks prior to study screening will be recorded. All other medications taken during the 4 weeks prior to study screening will be recorded. Concomitant medications will be recorded during the main study phase and extended treatment phase of the study, and during the associated FU and ET FU periods.

Prior and concomitant non-antifungal medication to be reported throughout the course of the study as follows:

- All chemotherapy regimens (summary only) taken during 12 weeks prior to screening.
- All T-cell immune-suppressants (e.g. cyclosporine, tacrolimus, monoclonal antibodies or nucleoside analogues) given within 90 days prior to screening or any dosing prior to study entry that support the host factor criteria “Treatment with other recognized T-cell immunosuppressants” at the time of the initial diagnosis of the fungal infection.
- All other medications given within 4 weeks prior to screening or any dosing prior to study entry that support the host factor criteria “Prolonged use of Corticosteroids”.
- All medications taken during the treatment period.
- All medications taken during the 4-week post-treatment period.

All concomitant medications taken by the patient during the study (including the 4-week FU period) are to be recorded in the appropriate section of the eCRF, noting the name, dose, duration and indication of each drug. Concomitant antifungal medication must be recorded. Non-medication procedures (e.g., radiation therapy, surgery), including all treatment for IFD, and any changes to a concomitant medication or other intervention should also be recorded in the appropriate section(s) of the eCRF.

5.9.1 Excluded Medications

Concomitant administration of teriflunomide and leflunomide is prohibited as the risk for combined hepatotoxicity with these inhibitors of human DHODH is not known. There are no other absolutely prohibited or contraindicated medications. [REDACTED]

5.9.1.1 Agents with a potential effect on the QT interval

Concentration-QTc effect modelling using data from a healthy volunteer study, where F901318 was administered orally for 18 days at a maintenance dose level of 240 mg twice daily, has shown no evidence of a clinically significant effect of F901318 on cardiac repolarization at a supratherapeutic exposure. The pharmacokinetic-pharmacodynamic model predicted no clinically significant effects on QTc at the mean steady state C_{max} of 4.8 $\mu\text{g/mL}$ achieved in this study (mean C_{max} of < 4 $\mu\text{g/mL}$ is predicted in Study F901318/0032). However, as Study F901318/0032 is the first clinical study in patients with invasive fungal infections, precautionary measures will be taken.

Prior to study start, if a patient is receiving a stable dose of a medication with the potential to prolong the QT/QTc interval and the patient has QTcF < 500 msec, they will be eligible for enrolment in the study.

Guidance for management of the initiation of a QT-prolonging agent after enrolment is currently under review. At present initiation of treatment with any medication with the potential to prolong the QT/QTc interval after treatment with F901318 has commenced is only permitted after discussion with the MM. Based on guidance contained in the medical monitoring plan current at the time, the MM will advise on required ECG monitoring (if any). Such monitoring may include:

[REDACTED]

[REDACTED]

[REDACTED]

5.9.1.2 *Interaction of F901318 with Concomitant Medication*

Medications with the potential for meaningful DDIs with F901318 are summarized in the IB and in this section. In brief, any agent that either inhibits CYP-mediated drug clearance (might reduce clearance of F901318) or that is cleared by CYP3A4 (levels might be increased by F901318) should be used with care. [REDACTED]

[REDACTED]. All other medications with potential for DDIs should be approached on a case-by-case basis in consultation with the MM.

In *in vitro* studies, F901318 is a substrate for CYP1A2, CYP2D6, CYP2C19, CYP3A4, CYP2C9, and CYP2C8, with metabolism being more significant for 3A4, 2C9, and 2C8. F901318 is not an inducer of any CYP enzyme. F901318 is a weak inhibitor of CYP3A4 (clinical studies have shown an approximate 1.6-fold elevation of midazolam exposure). F901318 also shows potential for inhibition of the P-gp, BCRP, and BSEP transporters in *in vitro* studies, and whilst the potential for drug interactions is thought low, careful monitoring may be needed for sensitive substrates of these transporters which have narrow therapeutic windows. The specific combination of F901318 and fluconazole (CYP3A4 and CYP2C9 inhibitor) has been studied in man and fluconazole has been shown to increase mean AUC₀₋₁₂ and C_{max} of F901318 by 2.0 and 1.7-fold, respectively.

[REDACTED] In addition, F901318 could increase the exposures of compounds metabolized by CYP3A4.

The Investigator is advised to consult with the MM on concomitant medications that either are metabolized by the liver or that influence hepatic metabolism, [REDACTED]. Specific data on other drug-drug combinations is being continuously developed. [REDACTED]

5.9.1.3 *Co-Dosing with Strong CYP Inducers*

Due to potential DDIs with F901318 and CYP inducers, co-dosing with these agents may lead to CYP induction that could dramatically reduce F901318 levels. [REDACTED]

[REDACTED] Consultation with the MM is advised if the combination of F901318 with a CYP inducer cannot be avoided.

Strong CYP inducers include :

- Phenytoin
- Rifampin
- Flucloxacillin (Kennedy 2015; Muilwijk 2017)
- Dicloxacillin
- Nafcillin
- Carbamazepine
- Ritonavir (*note that ritonavir is both an inducer and an inhibitor*)
- Enzalutamide
- Mitotane
- St John's wort

See also further guidance on strong CYP inducers at the FDA website:

(<https://www.fda.gov/drugs/developmentapprovalprocess/developmentresources/druginteractions/labeling/ucm093664.htm>).

If a medication that potentially induces CYP is required, consultation with the MM is advised. An extra visit for Unscheduled Trough PK sampling for rapid analysis will be required after starting or stopping such concomitant medication, to support evaluation of the impact of the potential DDI.

The Unscheduled Trough PK samples will be sent to the regional hub for rapid trough PK analysis of F901318 to enable assessment of potential DDIs.

